8.5.3 Demographic and safety analyses

Data for Parts A and Part B will be analysed separately.

For qualitative demographic and safety variables, the population size (N for sample size and n for available data) and the percentage (of available data) for each class of the variable will be presented. Quantitative variables will be summarised using descriptive statistics, including n, mean, SD, median, minimum, and maximum values. Where appropriate, assessments will be summarised by visit. All data will be summarised and listed appropriately.

The number of patients screened and included in the safety analysis set will be summarised. Demographic and baseline characteristics will be summarised and listed for the safety analysis set.

Treatment duration will be summarised. Treatment duration is based on the dates of first and last dose of any study treatment.

Study day will be calculated as follows:

- Days prior to first dose: Study day=date – first dose date.
- Days on or after first dose: Study day=date – first dose date+1.

Where day is missing from the date, but is required in the calculation of time to informed consent, day will be imputed as 01, ie, 1st of the month. Otherwise no imputations will be made for any missing data, unless agreed by the study team.

Safety profiles will be assessed in terms of AEs, vital signs (including blood pressure and pulse rate), ECG, laboratory data (clinical chemistry, haematology and urinalysis) and physical examinations.

Appropriate summaries of AEs, laboratory data, vital signs, and ECGs will be produced. Adverse events will be summarised separately for Parts A and B of the study. Laboratory data, vital signs, physical examinations, temperature, and ECGs will be summarised for

Parts A and B. Summaries will be presented for scheduled visits only. Any unscheduled assessments will be listed. The baseline value is defined as the latest result obtained prior to the start of study treatment.

The number of patients experiencing AEs following administration of AZD9291 and rifampicin, as well as the number of AEs experienced, will be summarised. Adverse events will be classified using the Medical Dictionary for Regulatory Activities (MedDRA) system of nomenclature (preferred term and system organ class). Adverse events reported before administration of AZD9291 will be listed only and be referred to as “pre-treatment”. Treatment emergence will be defined for each part of the study (A and B).

For each part (A and B), a treatment-emergent AE will be defined as an AE with the start date and time on or after the first dose date of study treatment and time (Part A) or first dose date (Part B) up to (and including) 30 days after the last dose date. Similarly, the number of patients experiencing SAEs, other significant AEs (OAEs), AEs that led to withdrawal, AEs that led to death, and treatment-related AEs and the number of such events will be summarised by part and period within part, as applicable. Adverse events with a start date and time in Part A that are ongoing at the start of Part B of the study will be summarised separately.

All AE data will be listed for all patients. In addition, SAEs, OAEs, and AEs that led to withdrawal or death, and treatment-related AEs will be listed.

Laboratory data (haematology, clinical chemistry and urinalysis) will be summarised and listed. Shift tables will be provided for select tests, where shift from baseline to the worst value within each part of the study and overall will be summarised. Laboratory data outside the reference ranges should be indicated in the listings.

Concomitant medications will be summarised by the coded terms. The number of patients receiving a medication will be summarised overall and for each part of the study. A medication taken during the course of the study is considered concomitant. A patient is only counted once even if they receive the medication more than once within that Part of the study.

The impact of any important protocol deviations, missing data and the use of rescue or concomitant medication on the robustness of study results will be investigated and any methods employed to deal with these will be documented.

Additional tables, figures, or listings, or combinations of Part A and Part B data may be produced to aid interpretation.

Further details of summaries of the safety data will be given in the SAP.

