3.9.1 Procedures for discontinuation of a patient from investigational product

At any time, patients are free to discontinue IP or withdraw from the study (ie, IP and assessments – see Section 3.10), without prejudice to further treatment. A patient that decides to discontinue IP will always be asked about the reason(s) and the presence of any AEs. If possible, they will be seen and assessed by an Investigator(s). Adverse events will be followed up (See Section 6); and all study drugs should be returned by the patient.

In Part A and Part B, any patient discontinuing IP should be seen at 30 days (± 7 days) after their last dose for the evaluations outlined in the study plan (see Table 1 and Table 2). After discontinuation of study drug, the Investigator will perform the best possible observation(s), test(s), and evaluation(s), as well as give appropriate medication and all possible measures for the safety of the patient. In addition, they will record on the eCRF the date of discontinuation, the reasons, manifestation, and treatment at the time of discontinuation. If patients discontinue IP, the AstraZeneca monitor or its representative must be informed immediately. The patient should return all IP.

After discontinuation of the study drug in Part A or Part B, all ongoing AEs or SAEs must be followed until resolution unless, in the Investigator's opinion, the condition is unlikely to resolve due to the patient's underlying disease, or the patient is lost to follow-up (see Sections 6.3.1 and 6.3.2). All new AEs and SAEs occurring during the 30 calendar days after the last dose of study drug must be reported (if SAEs, they must be reported to AstraZeneca or its representative within 24 hours as described in Section 6.4) and followed to resolution as above. Patients should attend for a follow-up visit 30 (± 7) days after discontinuing study drug to collect and/or complete adverse event (AE) information and collect IP. Any untoward event occurring subsequent to the 30-day follow-up AE reporting period that the Investigator assesses as possibly related to the study drug should also be reported as an AE.

At the end of Part B, patients may continue to receive IP as continued access and undergo follow up as part of their normal routine clinical care. After discontinuation of the IP in the continued access phase of the study, patients should be followed for 30 days to follow up any existing SAEs and monitor for any new SAEs that may be related to IP.

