6.1 Definition of adverse events

An AE is the development of an undesirable medical condition or the deterioration of a pre-existing medical condition following or during exposure to a pharmaceutical product, whether or not considered causally related to the product. An undesirable medical condition can be symptoms (eg, nausea, chest pain), signs (eg, tachycardia, enlarged liver) or the abnormal results of an investigation (eg, laboratory findings, ECG). In clinical studies, an AE can include an undesirable medical condition occurring at any time, including run-in or washout periods, even if no study treatment has been administered.

The term AE is used to include both serious and non-serious AEs.

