6.3 Recording of adverse events

6.3.1 Time period for collection of adverse events

Adverse Events will be collected from the time of signature of informed consent, throughout the Part A treatment periods, Part B, and the follow-up period.

All SAEs will be recorded from the time of informed consent.

Patients entering Part B will be able to continue taking AZD9291 for as long as they are receiving clinical benefit; however study assessments will cease approximately 12 months after the last patient enters Part B. After Part B, there may be some patients remaining on study treatment via the continued access part of this protocol. For these patients who are continuing to receive AZD9291 and being followed as part of routine clinical care, AstraZeneca will collect limited information only (see Section 7.8).

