6.3.3 Variables

The following variables will be collected for each AE;

- AE (verbatim)
- The date and time when the AE started and stopped
- Changes in CTCAE grade (for skin reactions and diarrhoea only); maximum CTCAE grade for all other AEs
- Whether the AE is serious or not
- Investigator causality rating against the IP and other study drug (ie, rifampicin) (yes or no)
- Action taken with regard to IP
- Outcome.

In addition, the following variables will be collected for SAEs:

- Date AE met criteria for serious AE
- Date Investigator became aware of serious AE
- AE is serious due to
- Date of hospitalisation
- Date of discharge
- Probable cause of death
- Date of death
- Autopsy performed
- Causality assessment in relation to Study procedure(s)
- Causality in relation to other medication
- Description of AE.

It is important to distinguish between serious and severe AEs. Severity is a measure of intensity whereas seriousness is defined by the criteria in Section 6.2. An AE of severe intensity need not necessarily be considered serious. For example, nausea that persists for several hours may be considered severe nausea, but not a SAE unless it meets the criteria shown in Section 6.2. On the other hand, a stroke that results in only a limited degree of disability may be considered a mild stroke but would be a SAE when it satisfies the criteria shown in Section 6.2.

The grading scales found in the revised CTCAE version 4 will be utilised for all events with an assigned CTCAE grading. For those events without assigned CTCAE grades, the recommendation in the CTCAE criteria that converts mild, moderate and severe events into CTCAE grades should be used. A copy of the CTCAE version 4 can be downloaded from the Cancer Therapy Evaluation Program website (<http://ctep.cancer.gov>).

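### Treatment emergence is judged by AE start date alone, so an AE that began in screening and worsened after dosing can go unsummarised

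*Protocol*

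**What the plan says.** Collection starts well before dosing. Protocol section 6.3.1 states: "Adverse Events will be collected from the time of signature of informed consent". In Table 1, screening runs from Day -28 to Day -2, with a further visit on Day -1.

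The analysis rule is in section 8.5.3. For each part, "a treatment-emergent AE will be defined as an AE with the start date and time on or after the first dose date", and the window runs "up to (and including) 30 days after the last dose date". For events before dosing the same section says: "Adverse events reported before administration of AZD9291 will be listed only", under the label pre-treatment.

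The recording rule is in section 6.3.3. Each AE has a start and a stop date and time. Changes in grade are collected for skin reactions and diarrhoea, and "maximum CTCAE grade for all other AEs".

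The definition of an AE in section 6.1 includes "the deterioration of a pre-existing medical condition following or during exposure to a pharmaceutical product".

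**The concern.** Examining safety and tolerability is an objective of both parts (section 2.3). The study has no control arm and about 38 patients, so the AE counts and percentages are the main AE evidence.

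A start-date definition works when nothing is recorded before dosing, or when every worsening opens a new record. Here neither is assured. AEs are collected from consent, and a screening AE may simply be carried forward under its original start date when it becomes worse on treatment. Two things then follow. The worsening is missing from the counts that a reader would take as the on-treatment AE profile. In addition, the listing shows an AE labelled pre-treatment with a grade that was reached on treatment.

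**Working it through.** The protocol states no figure on this point, so the check follows one record through the rules.

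**Hypothetical record.** Nausea, Grade 1, starts on Day -10 and reaches Grade 3 on Day 20.

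1. Is it collected? Yes. Day -10 is after consent (section 6.3.1).
2. Is the worsening an AE? Yes, by section 6.1, because a pre-existing condition deteriorated during exposure. Section 6.3.6 is in the same spirit: aggravated, clinically relevant findings at physical examination are reported as AEs.
3. How is it stored? Section 6.3.3 asks for one start, one stop and a maximum grade. No section requires a new record for the worsening. If the site updates the existing record, it reads: start Day -10, maximum Grade 3.
4. Is it treatment-emergent? No. The start date precedes the first dose, and section 8.5.3 tests nothing else.
5. Where does it appear? It was reported before AZD9291, so section 8.5.3 places it in a listing as pre-treatment, with Grade 3.
6. Can the analysis recover it? Not from this record. The maximum grade carries no date, so the AE data do not show whether Grade 3 came before or after the first dose.

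If at step 3 the site instead opens a new record starting on Day 20, step 4 gives the opposite answer and the event is counted. The outcome depends on data-entry practice at about 16 sites (section 1.4).

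**Skin reactions and diarrhoea.** Section 6.3.3 does ask for grade changes for these. However, sections 6.7.1 and 6.7.2 describe that capture for Part B, while a screening AE would first worsen in Part A. Rash and diarrhoea are among the most common AEs named in section 1.3. Even where grade changes are captured, the definition in section 8.5.3 does not use them.

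**Size, on assumed rates.** The documents give neither rate. Assume that 20% to 40% of patients have an AE starting between consent and Day 1, that 10% to 25% of those worsen in grade on treatment, and that no site opens a new record.

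- Low: 0.20 × 0.10 = 0.02, and 0.02 × 38 = 0.8 patients.
- High: 0.40 × 0.25 = 0.10, and 0.10 × 38 = 3.8 patients.

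That is about 1 to 4 patients. Each patient is 1/38 = 2.6 percentage points of any AE percentage.

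**The case against.** **Nothing forces a single record.** Section 6.3.3 only lists the variables kept for each AE, and section 6.1 would let a site enter the deterioration as an AE of its own. Section 5 also refers to eCRF instructions that are not shown. This stands, and it is why the point is that worsening can go unsummarised, not that it must. It does not remove the point, because the protocol permits a new record without requiring it, and a maximum-grade field invites updating the old one.

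**Much is covered elsewhere.** All AEs are listed. Laboratory tests and vital signs are summarised directly, with shift tables for selected laboratory tests. AEs that start in Part A and continue into Part B get their own summary. Exclusion criterion 5 bars most unresolved toxicity from prior therapy above Grade 1. Events unequivocally due to progression are not AEs (section 6.3.8). All of this stands and reduces the number of records at risk. None of it summarises a symptomatic AE that began in screening and worsened in Part A.

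**The statistical analysis plan may complete the definition.** Section 8.5.3 leaves further detail of the safety summaries to it. But on this point the protocol is not silent: it states a definition and a listing rule. No later analysis rule can supply a date that was not collected.

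**A stronger reading concerns late events.** Section 3.9.1 requires "Any untoward event occurring subsequent to the 30-day follow-up AE reporting period that the Investigator assesses as possibly related to the study drug" to be reported as an AE, and the follow-up visit may fall on day 30 + 7 = 37 after the last dose, whereas the treatment-emergent window closes on day 30. A reader might infer that such events drop out of the treatment-related summary, or out of every AE summary. The text does not support that. The summaries of AEs following administration, of SAEs and of treatment-related AEs are not expressly limited to treatment-emergent AEs. The linking word after the definition in section 8.5.3 is too ambiguous to be read as an exclusion.

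**Conclusion.** The concern holds for AEs with onset in screening. Section 8.5.3 has no worsening criterion and sends AEs reported before dosing to a listing, and section 6.3.3 keeps an undated maximum grade for most AEs. Together they allow an on-treatment deterioration, which section 6.1 counts as an AE, to be left out of the summaries and labelled pre-treatment. This depends on one condition: that the worsening is kept in the original record.

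The scale is modest. The estimate of 1 to 4 patients rests wholly on assumed rates and on no site opening a new record, so it is illustrative and leans high. The events remain visible in listings, the safety analysis is descriptive, and the primary pharmacokinetic comparison is untouched. It is still worth correcting, because the recording half cannot be repaired once the data are in.

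**What to change.** - In section 8.5.3, define a treatment-emergent AE as one that starts, or worsens in CTCAE grade, on or after the first dose and up to 30 days after the last dose. Limit the pre-treatment listing rule to AEs that do not worsen after the first dose.
- In section 6.3.3 and the eCRF instructions, require any post-dose worsening of an AE that began before dosing to be entered as a new record with its own start date and grade.
- Because emergence is defined separately for each part, say that AEs carried from Part A into Part B stay in the separate summary already planned, so that they are not counted twice.

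The cost is a few sentences of text, one data-entry instruction to sites, and slightly higher AE counts. No dosing or clinical rule changes.

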1.4 Study design

This is a Phase I, open-label, non-randomised, two-part study in patients with EGFRm+ NSCLC who have progressed on an EGFR TKI. Part A will assess the effect of rifampicin on the PK parameters of AZD9291 and metabolites AZ5104 and AZ7550 following multiple oral dosing of both rifampicin and AZD9291 in a fasted state.

Part B will allow patients further access to AZD9291 after the PK phase (Part A) and will provide for additional safety data collection.

This study will be conducted at approximately 16 sites across Asia, North America and Western Europe with approximately 38 patients enrolled and dosed to achieve at least 30 evaluable patients. Additional patients may be enrolled to ensure the minimum number of evaluable patients. For a patient to be evaluable the patient must have completed the required PK collections for the primary comparison (AZD9291 and rifampicin combined [Period 2] compared to AZD9291 administered alone [Period 1]).

Part A

[figure not shown]
Part A is a non-randomised, open-label, 3-period design. A study flow chart for Part A is presented in [Figure 1](#). Patients will receive AZD9291 80 mg once daily for 77 days (Days 1 to 77). Patients will also receive oral daily doses of rifampicin for 21 days (Days 29 to 49) concurrently with AZD9291.

Part B

On completion of Part A, patients may continue to take AZD9291 tablets (80 mg once daily) in Part B if they and the Investigator agree that this is appropriate. Patients should start Part B immediately (ie, 24 hours) after the last dose received in Part A (Day 78 after the 24-hour sample collection). Patients will have weekly clinic visits for the first 4 weeks; thereafter visits will be every 4 weeks. Safety assessments will be collected and there will be no formal evaluation of efficacy. Patients' medical/oncological care will be according to local clinical practice. Part B will be of approximately 12 months' duration from the date the last patient enters this part of the study (allowing for any scheduled Part B follow-up assessments).

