2.3 Safety objectives

Part A: To examine the safety and tolerability of AZD9291 in patients with EGFRm+ NSCLC in the presence and absence of co-administered rifampicin.

Part B: To examine the safety and tolerability of AZD9291 following extended administration in patients with EGFRm+ NSCLC.

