7.2 Dose and treatment regimens

7.2.1 Part A

In Part A, each patient will receive a once daily 80 mg oral dose of AZD9291, on Days 1 to 77. From Days 29 to 49 each patient will receive rifampicin 600 mg once daily. Rifampicin will be taken concomitantly with AZD9291. All treatments (AZD9291 and rifampicin) will be administered fasted from at least 2 hours before dosing to at least 2 hours after dosing. Water is allowed as desired except for 1 hour before and after AZD9291 administration on Days 28, 49, and 77. There are no restrictions for water intake on any other study days. The study treatments should be swallowed whole with approximately 240 mL of water, and not chewed, crushed, dissolved or divided.

On clinic days on which PK samples are scheduled to be taken, the dosing should be delayed until arrival at the clinic and until the pre-dose PK samples have been taken. Patients should not take their IP until instructed to do so by site personnel.

If a patient vomits on Day 28 or Day 49 within approximately 6 hours of dose administration, the AstraZeneca representative should be contacted for advice regarding the evaluability of the patient or whether the patient may return to the clinic on a subsequent day to repeat the treatment. If a patient is discontinued from Part A, the Investigator may contact an AstraZeneca representative to determine if it is appropriate for the patient to proceed into Part B.

If a patient vomits within approximately 6 hours of dose administration on Day 77, PK sample collection may be discontinued after the event but the safety assessments should continue as

per the study schedule. The patient may proceed to Part B after completion of the required safety assessments, if the patient and Investigator agree that this is appropriate.

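### The Part A laboratory shift table pools rifampicin and rifampicin-free periods, so on its own it cannot show in which condition patients worsened

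*Protocol*

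**What the plan says.** Section 2.3 gives the Part A safety objective: "To examine the safety and tolerability of AZD9291 in patients with EGFRm+ NSCLC in the presence and absence of co-administered rifampicin". Section 1.4 describes the structure: "Part A is a non-randomised, open-label, 3-period design". Section 7.2.1 places rifampicin in the middle period only: "From Days 29 to 49 each patient will receive rifampicin 600 mg once daily". AZD9291 runs throughout, Days 1 to 77.

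Section 8.5.3 provides laboratory shift tables for selected tests, "where shift from baseline to the worst value within each part of the study and overall will be summarised". The baseline is common to all of Part A: "The baseline value is defined as the latest result obtained prior to the start of study treatment".

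The same section treats SAEs, other significant AEs, AEs leading to withdrawal or death, and treatment-related AEs at a finer level; these "will be summarised by part and period within part, as applicable". It also says "Where appropriate, assessments will be summarised by visit", provides for listings with out-of-range laboratory values marked, allows additional tables, and leaves further detail of the safety summaries to the SAP, which was not available for this review.

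**The concern.** The safety question in Part A concerns two conditions, and the shift table is the one specified laboratory summary that counts patients by how far they moved from baseline. Its window is the whole of Part A. A transaminase rise on Day 14 and one on Day 42 land in the same cell. A value already raised on AZD9291 alone by Day 28 looks the same as a rise that first appears after rifampicin is added.

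This is a level the protocol states, not one it leaves open. Period is used a few lines away for the named adverse event categories. At stake is whether the Part A report can say, from its shift tables, how many patients worsened with rifampicin and how many without.

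**Working it through.** There is no stated figure to reproduce; the check compares windows and counts visits.

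**1. Windows side by side.**

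| Output (section 8.5.3) | Level stated |
|---|---|
| Laboratory shift to worst value | Part, and overall |
| SAEs, other significant AEs, AEs leading to withdrawal or death, treatment-related AEs | Part, and period within part |
| Other assessments | By visit, where appropriate |

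Only the first row gives one value per patient that spans both conditions of Part A.

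**2. Laboratory visits per period.** Table 1 schedules haematology and biochemistry on treatment at:
- Period 1: Days 7, 14, 21, 28 = 4
- Period 2: Days 35, 42, 49 = 3
- Period 3: Days 56, 63, 70, 78 = 4

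Table 5 lists 5, 3 and 4 samples. The fifth in Period 1 is the Day -1 sample before dosing, so the two tables agree. The total on treatment is 4 + 3 + 4 = 11, of which 3/11 = 27% fall in rifampicin dosing and 8/11 = 73% outside it. Each scheduled visit belongs to one period, so a by-period shift table needs no new sample.

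**3. What the pooled table can hide (illustration on assumed risks).** Let q be the chance of an abnormal value at a visit without rifampicin, and RR the factor by which rifampicin changes it. Treat visits as independent. Then

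Part A shift rate = 1 − (1 − q)^8 × (1 − q·RR)^3

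Period 1 or 3 rate = 1 − (1 − q)^4; Period 2 rate = 1 − (1 − q·RR)^3

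With q = 3% and RR = 1, the Part A rate is 1 − 0.97^11 = 28.5%. Solving for the q that gives the same Part A rate under other values of RR:

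| RR | q | Period 1 | Period 2 | Period 3 | Part A |
|---|---|---|---|---|---|
| 1 | 3.00% | 11.5% | 8.7% | 11.5% | 28.5% |
| 3 | 1.93% | 7.5% | 16.4% | 7.5% | 28.5% |
| 5 | 1.42% | 5.6% | 19.8% | 5.6% | 28.5% |

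The first row follows from 1 − 0.97^4 = 11.5% and 1 − 0.97^3 = 8.7%. The pooled table is identical in all three cases; a by-period table is not. The protocol gives neither q nor RR, so these rows show only that the ambiguity is possible, not how large it would be here.

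**4. Do the by-period AE tables fill the gap?** Only in part. Under section 6.3.6, deterioration in a protocol-mandated laboratory parameter is reported as an AE only if it meets an SAE criterion or is the reason for stopping treatment; accompanying signs or symptoms are reported in their own right. A non-serious rise without symptoms that does not stop treatment would generally appear only in the laboratory outputs.

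**The case against.** The layout of shift tables is usually settled in the SAP. Section 8.5.3 defers detail there, permits extra tables, and does not say that shifts will be shown by part only. A by-period shift table in the SAP would contradict nothing. By-visit summaries separate the periods cleanly and include SD, minimum and maximum as well as mean and median. With about 38 patients and 11 samples each (38 × 11 = 418 sets of results), the timing of each abnormality can be read from the listings. Serious or treatment-ending laboratory changes reach the AE tables, which are split by period.

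Most of this stands, and it keeps the point small. It does not remove it: the protocol chose a level, and that level does not match the objective. By-visit statistics and listings do not count patients who worsened per condition.

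Some stronger readings should be resisted:
- A reader might infer that laboratory safety with and without rifampicin cannot be assessed at all. The by-visit summaries and listings show otherwise.
- A reader might take 73% as the share of worst values arising without rifampicin. It is 8/11, and carries over to worst values only if risk is equal at every visit. It restates the schedule and measures no bias.
- A reader might take the objective as a formal comparison. It is to examine safety, and no test is planned. Section 1.2 justifies the sequential design by PK onset, extent and offset of induction, not by a laboratory contrast.
- A reader might call the single pre-treatment baseline an error. It is a legitimate choice.

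**Conclusion.** The point holds for the Part A shift table taken alone: its window pools the two conditions named in the Part A safety objective, and it cannot show in which of them a patient worsened. This rests on the wording of section 8.5.3 and the period structure, not on the assumed risks in the illustration. It is a modest mismatch between an objective and one of several laboratory outputs, and it affects no PK conclusion.

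By-period shifts would not isolate a rifampicin effect. The order of periods is fixed, so rifampicin is confounded with time on AZD9291, and early Period 3 follows the offset of rifampicin and is not a clean rifampicin-free condition. The tables would remain descriptive.

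**What to change.** In section 8.5.3, after the by-part and overall wording for shift tables, add: *and, for Part A, within each period*. Shift from the pre-treatment baseline to the worst value would then also be shown for Periods 1, 2 and 3. Keep the by-part and overall tables. As an optional supplement, show the Period 2 shift from the Day 28 value, which separates new rises from those already present before rifampicin. Label the tables descriptive and note the fixed sequence.

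The cost is a few more tables from samples already scheduled, with no change to visits, blood volume or patient numbers. If the SAP already contains by-period shifts, only the protocol wording needs to be aligned.
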